8.4.1. Pregnancy Reporting

Pregnancy of a female subject or the female partner of a male subject occurring while the subject is on treatment or within 4 weeks after the subject's last dose of study drug are considered expedited reportable events. Study drugs—Lenalidomide, dexamethasone, and carfilzomib—are to be discontinued immediately. The pregnancy must be reported within 24 hours of the Treating Investigator's knowledge of the pregnancy by phone and facsimile using the SAE form to the University of Chicago CRA either by fax or by email. The Treating Investigator must inform the University of Chicago in writing by email or facsimile of any pregnancy within 24 hours / 1 business day at the latest on the following workday of being aware of the event. The University of Chicago must report pregnancy as an SAE directly to BMS and Amgen using expedited reporting procedures listed in Section 8.4 and 8.4.1.

Pregnancy Reporting by Lead Principal Investigator to BMS

If, following initiation of the investigational product, it is subsequently discovered that a study subject is pregnant or may have been pregnant at the time of investigational product exposure, including during at least 5 half lives after product administration, the investigational product will be permanently discontinued in an appropriate manner (e.g. dose tapering if necessary for subject safety).

The investigator must immediately notify [contact] of this event via the Pregnancy Surveillance Form in accordance with SAE reporting procedures.

Follow-up information regarding the course of the pregnancy, including perinatal and neonatal outcome and, where applicable, offspring information must be reported on the Pregnancy Surveillance Form [provided upon request from BMS]

Any pregnancy that occurs in a female partner of a male study participant should be reported to BMS. Information on this pregnancy will be collected on the Pregnancy Surveillance Form.

Pregnancy Reporting by Lead Principal Investigator to Amgen

Report Pregnancy and potential infant exposure including Lactation, within ten (10) calendar days of the Lead Principal Investigator awareness. Provide to Amgen the SAE reports associated with pregnancy.

Subjects, spouses, or partners will be followed through the outcome of the pregnancy.

If the outcome of the pregnancy meets a criterion for immediate classification as an SAE—spontaneous abortion (any congenital anomaly detected in an aborted fetus is to be documented),

stillbirth, neonatal death, or congenital anomaly—the Treating Investigator should repeat the procedures for expedited reporting of SAEs as outlined above.

9. INVESTIGATIONAL MEDICINAL PRODUCT

9.1. Elotuzumab

9.1.1. **Description**

Elotuzumab (BMS- 901608; formerly known as HuLuc63) is a humanized recombinant monoclonal IgG1 antibody product directed to human CS1 (CD2-subset-1, also known as CRACC and SLAMF7), a cell surface glycoprotein that is highly expressed in MM cells.

9.1.2.**Form**

Elotuzumab for injection has been developed to be used as an intravenous (IV) infusion for the clinical studies. The drug product will be reconstituted prior to administration.

Product Description / Class and Dosage Form	Potency	Blinded or Open Label	Packaging / Appearance	Storage Conditions (per label)
Elotuzumab Powder for Solution for Infusion	400 mg/vial or 300mg/vial	Open Label	20 mL Vial/ Sterile, white to off-white, preservative-free, lyophilized cake	Store at 2°C - 8°C

9.1.3. Storage and Stability

The product storage manager should ensure that the study drug is stored in accordance with the environmental conditions (temperature, light, and humidity) as determined by the sponsor. If concerns regarding the quality or appearance of the study drug arise, do not dispense the study drug and contact the sponsor immediately.

The lyophilized elotuzumab drug product should be stored at 2° to 8° C. Prior to administration the drug product must be reconstituted with Sterile Water for Injection, USP, and then further diluted in 0.9% sodium chloride normal saline, USP, as per the instructions in section 9.1.6. After the dose is diluted in normal saline, it must be administered within 8 hours if stored at room temperature. If a delay is anticipated, the prepared dose may be refrigerated at 2° to 8° C for up to 24 hours. If stored under refrigerated conditions, the prepared study drug solution should be equilibrated to room temperature (process takes 2 - 2.5 hours) and the container must be gently inverted to mix well before administration. Do not use the accelerated warming method. If administration is delayed beyond the specified time, the prepared dose solution must be discarded, and the reason documented by the pharmacist in study drug accountability records.

The dose of elotuzumab to be administered to a subject will be calculated by multiplying the subject's weight (kg) by 10 mg/kg. The subject's pre-dose weight at screening will be used to calculate the dose for each cycle, unless there is a change in weight of \geq 10%. Each dose should be infused as per instructions in Section 6.3.

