6.10.1. Elotuzumab Infusion Reactions

The first dose of elotuzumab will be administered following pre-medications to each subject as an IV infusion, using an automated infusion pump set at an initial rate of 0.5mL per minute (30 mL/hour). If the subject does not have an infusion reaction within 30 minutes, escalate the infusion rate by 0.5 mL per minute. If the subject still does not have an infusion reaction within 30 minutes, escalate the infusion rate to a maximum of 2 mL per minute (120 mL/hour).

The second dose of elotuzumab should be initiated at an infusion rate of 3 mL per minute if no infusion reactions were reported with the first elotuzumab infusion. If the subject does not experience an infusion reaction during the first 30 minutes of the second dose of elotuzumab, escalate the infusion rate by 1.0 mL per minute to a maximum infusion rate of 4 mL per minute.

The third and fourth dose of elotuzumab should be initiated at an infusion rate of 5 mL per minute if no infusion reactions were reported with previous elotuzumab infusions.

Guidelines for Elotuzumab Infusion in Subjects with Infusion Reactions

Grade 1 Infusion Reaction: Grade 1 elotuzumab infusion-related reactions by definition do not require intervention; however, increased monitoring is recommended

Grade 2 or 3 Infusion Reaction: Infusion reactions during the elotuzumab infusion: For a Grade 2 or 3 elotuzumab infusion-related reactions, the infusion must be interrupted. The subject should be treated as clinically indicated with one or more of the following medications or

interventions: antiemetics, antihistamines, analgesics, corticosteroids, leukotriene inhibitors, oxygen inhalation, epinephrine, bronchodilators, or other supportive measures as indicated.

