9.1.6. Preparation

Elotuzumab for Injection, 400 mg/vial and Elotuzumab for Injection, 300 mg/vial.

Each vial of Elotuzumab for Injection, 400 mg/Vial and Elotuzumab for Injection, 300 mg/Vial should be reconstituted with sterile water for injection (SWFI) at the clinical compounding site. The lyophilized powder should dissolve in less than 10 minutes. Once the reconstitution is completed, withdraw 16 mL from the 400 mg/vial presentation or 12 mL from the 300 mg/vial presentation for dilution with 0.9% sodium chloride injection (NS) to result in an elotuzumab concentration from 1.0 mg/mL to no higher than 6.0 mg/mL in a polyvinyl chloride or polyolefin infusion bag. Five percent (5%) Dextrose injection (D5W) may be used as a diluent in place of 0.9% sodium chloride injection. During drug product preparation, vigorous mixing or shaking is to be avoided. The infusion is to be administered through a sterile, non-pyrogenic, low protein binding in line filter (with a pore size of 0.2-μm to 1.2-μm) using an automated infusion pump. Additionally, care must be taken to ensure the sterility of the prepared solution, as the drug product does not contain anti-microbial preservatives or bacteriostatic agents. A sufficient excess of drug product is included in each vial to account for withdrawal losses.

The infusion of the reconstituted and diluted solution of elotuzumab for injection prepared for dosing must be completed within 24 hours of reconstitution. If not used immediately, the infusion solution may be stored under refrigeration conditions, 2°C to 8°C (36°F to 46°F), and protected from light for up to 24 hours (a maximum of 8 hours of the total 24 hours can be at room temperature, 20°C to 25°C (68°F to 77°F), and room light). The drug solution should be equilibrated to room temperature and the container must be gently inverted to mix well before administration.

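### An elotuzumab bag refrigerated for the full 24 hours that 9.1.3 permits cannot meet the 24-hour completion limit in 9.1.6

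*Combined protocol and SAP*

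**What the plan says.** Section 9.1.3 (Storage and Stability) sets an 8-hour limit, counted from dilution, for a bag kept at room temperature. If a delay is expected, "the prepared dose may be refrigerated at 2° to 8° C for up to 24 hours"; no start is given for that period. A warming step follows: "If stored under refrigerated conditions, the prepared study drug solution should be equilibrated to room temperature (process takes 2 - 2.5 hours". Accelerated warming is barred. A dose delayed past a specified time is to be discarded, but the section does not say which time is meant. It sets no limit for finishing the infusion.

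Section 9.1.6 (Preparation) counts from reconstitution, which comes before dilution, and runs to the end of the infusion. Infusion of the diluted solution "must be completed within 24 hours of reconstitution". The section also allows refrigerated storage for up to 24 hours, with the proviso that "a maximum of 8 hours of the total 24 hours can be at room temperature". It asks for equilibration to room temperature without giving a duration, and it has no discard instruction. Dilution is "to result in an elotuzumab concentration from 1.0 mg/mL to no higher than 6.0 mg/mL".

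The infusion rates are in 6.4.1 and 6.10.1. The first dose runs at 0.5 mL/min for 30 minutes and 1 mL/min for 30 minutes, after which sites "escalate the infusion rate to a maximum of 2 mL per minute". The second dose runs at 3 mL/min for 30 minutes and then 4 mL/min. Later doses run at 5 mL/min. The dose is 10 mg/kg.

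**The concern.** Both sections govern the same bag. The storage allowance in 9.1.3 is as long as the whole window in 9.1.6, yet 9.1.3 puts a warming step of at least 2 hours after it, and the infusion follows that. A pharmacy that uses the full allowance would therefore be outside the other section's limit.

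What is at stake is product handling. Section 9.1.6 notes that the product contains no antimicrobial preservative, and section 4.2.2 plans five centers. With two clocks and an undefined discard time, a pharmacist cannot tell from the protocol whether a bag prepared the day before may still be given.

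**Working it through.** The 24-hour limit is a handling rule, so there is no derived figure to reproduce. The check adds up the times. The documents do not give body weights, so 50, 70 and 100 kg are assumed.

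**Inputs**
- Refrigeration up to 24 h; warming 2 to 2.5 h (9.1.3).
- Completion within 24 h of reconstitution; at most 8 h at room temperature; concentration 1.0 to 6.0 mg/mL (9.1.6).
- Dose 10 mg/kg (9.1.3); rates as in 6.4.1 and 6.10.1.

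**Step 1: full storage plus warming**

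24 + 2 = 26 h and 24 + 2.5 = 26.5 h before the infusion starts. This is 2 to 2.5 h past the limit, before preparation time is counted. Weight, concentration and dose number do not enter.

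**Step 2: infusion time**

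Volume V = 10 × weight / concentration, in mL.
- First dose: the first hour delivers 30 × 0.5 + 30 × 1 = 45 mL, so T = 60 + (V − 45)/2 minutes.
- Third and later doses: T = V/5 minutes.

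At 70 kg and 1 mg/mL, V = 700 mL. The first dose takes 60 + 655/2 = 387.5 min (6.46 h) and later doses take 140 min (2.33 h). At 6 mg/mL, V = 116.7 mL, and the times are 95.8 min (1.60 h) and 23.3 min (0.39 h).

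After 24 h of refrigeration, completion at 70 kg falls between 26 + 0.39 = 26.4 h (later dose, 6 mg/mL) and 26.5 + 6.46 = 33.0 h (first dose, 1 mg/mL).

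**Step 3: longest refrigeration compatible with the 24-hour limit**

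24 − warming − T, before subtracting preparation time. Each range spans 2.5 to 2 h of warming.

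| Weight | Concentration | First dose | Third and later doses |
|---|---|---|---|
| 50 kg | 6 mg/mL | 20.2–20.7 h | 21.2–21.7 h |
| 50 kg | 1 mg/mL | 16.7–17.2 h | 19.8–20.3 h |
| 70 kg | 6 mg/mL | 19.9–20.4 h | 21.1–21.6 h |
| 70 kg | 1 mg/mL | 15.0–15.5 h | 19.2–19.7 h |
| 100 kg | 6 mg/mL | 19.5–20.0 h | 20.9–21.4 h |
| 100 kg | 1 mg/mL | 12.5–13.0 h | 18.2–18.7 h |

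The second dose falls between the two columns. The overall range is 12.5 to 21.7 h. It measures the gap between the sections and is not a proposed limit.

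**Step 4: the 8-hour room-temperature cap (secondary)**

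Suppose that warming and infusion both count toward the cap; 9.1.6 does not say. For the first dose:
- Infusion alone: 60 + (V − 45)/2 = 480 min gives V = 885 mL, which is 88.5 kg at 1.0 mg/mL.
- After 2 h of warming, 360 min remain: V = 645 mL, or 64.5 kg.
- After 2.5 h of warming, 330 min remain: V = 585 mL, or 58.5 kg.

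Above these weights the 1.0 mg/mL dilution passes 8 h. More concentrated permitted dilutions do not: at 100 kg the crossing points are 1000/885 = 1.13 mg/mL without warming, and 1000/645 = 1.55 to 1000/585 = 1.71 mg/mL after it. At 100 kg and 1 mg/mL the second dose takes 4.29 h and later doses 3.33 h. Even with 2.5 h of warming these total 6.79 h and 5.83 h, inside the cap.

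Step 3 tests the 24-hour limit only. Its lowest entry (100 kg, 1 mg/mL, first dose) would also pass the 8-hour cap on this reading.

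**The case against.** The strongest reply is that 24 hours is a ceiling. Section 9.1.3 permits refrigeration up to that point and does not require it. A reader might infer that the time limits cannot all be met; the documents do not support that, because shorter storage meets the 24-hour terms of both sections. This stands, and it confines the conflict to the upper end of the allowance.

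Section 9.1.6 itself contains both 24-hour figures, and its reference to a total of 24 hours can be read as one combined window. Sections 9.1.3 and 9.1.4 also send the preparer to 9.1.6 for reconstitution and dilution. This makes a misreading less likely. It does not remove the allowance in 9.1.3, which is followed there by warming and by no completion limit.

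A reader might also infer that one section has a bag infused that the other has discarded. The only discard instruction is in 9.1.3. Section 9.1.6 makes a late infusion non-compliant but does not say what to do with the bag.

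On the 8-hour cap, a reader might infer that sites are driven past it. They are not: 1.0 mg/mL is the most dilute end of the permitted range, nothing requires it, and the cap stands in a sentence about storage. Nor do the documents link any of this to drug exposure before the cycle-8 endpoint; they do not say that a discarded bag means a missed dose.

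Finally, 6.4.1 refers to separate administration guidelines, which are not in the documents. As described there, they cover administration times, rates and preinfusion medication, not bag stability.

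**Conclusion.** The point holds in a limited form. The full 24-hour refrigeration allowance in 9.1.3 is unusable under 9.1.6, with an overrun of at least 2 to 2.5 hours whatever the weight, concentration or dose number. That result rests only on the protocol's own storage and warming times. The range of 12.5 to 21.7 hours also assumes 50 to 100 kg, uninterrupted infusion at the scheduled rates, and no preparation time. An infusion reaction that interrupts the infusion would shorten it.

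The 8-hour issue is secondary. It depends on a reading that 9.1.6 leaves open, and within the assumed weights it arises only at the first dose and near the dilute end of the range.

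This is a pharmacy-handling inconsistency in the protocol text, with no effect on sample size, alpha or power.

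**What to change.** The sponsor and the drug supplier should reconcile 9.1.3 and 9.1.6 into one in-use rule that:
- names one clock start (reconstitution or dilution) and one clock end (start or completion of infusion);
- says whether warming and infusion time count within the 24-hour and 8-hour limits;
- ties the discard instruction to that rule, in place of an undefined time.

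Which limit governs is for them to decide. The rule should be checked against the rates in 6.4.1 and 6.10.1, so that sites know whether each permitted dilution can be given inside it.

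The cost is amendment wording in the pharmacy sections. If the stricter reading is kept, some prepared bags will be discarded sooner.

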9.1.4. Handling

The lyophilized elotuzumab drug product should be stored at 2° to 8°C. Prior to administration the drug product must be reconstituted with Sterile Water for Injection, USP, and then further diluted in 0.9% sodium chloride normal saline, USP, as per the instructions in Section 9.1.6.

Qualified personnel, familiar with procedures that minimize undue exposure to themselves and the environment, should undertake the preparation, handling, and safe disposal of the chemotherapeutic agent in a self-contained and protective environment.

9.1.5. Availability

Bristol-Myers Squibb will supply elotuzumab. Elotuzumab is an investigational agent and will be supplied free-of- charge. Drug will be shipped to the pharmacy at the study site.

9.1.6. Preparation

Elotuzumab for Injection, 400 mg/vial and Elotuzumab for Injection, 300 mg/vial.

Each vial of Elotuzumab for Injection, 400 mg/Vial and Elotuzumab for Injection, 300 mg/Vial should be reconstituted with sterile water for injection (SWFI) at the clinical compounding site. The lyophilized powder should dissolve in less than 10 minutes. Once the reconstitution is completed, withdraw 16 mL from the 400 mg/vial presentation or 12 mL from the 300 mg/vial presentation for dilution with 0.9% sodium chloride injection (NS) to result in an elotuzumab concentration from 1.0 mg/mL to no higher than 6.0 mg/mL in a polyvinyl chloride or polyolefin infusion bag. Five percent (5%) Dextrose injection (D5W) may be used as a diluent in place of 0.9% sodium chloride injection. During drug product preparation, vigorous mixing or shaking is to be avoided. The infusion is to be administered through a sterile, non-pyrogenic, low protein binding in line filter (with a pore size of 0.2-μm to 1.2-μm) using an automated infusion pump. Additionally, care must be taken to ensure the sterility of the prepared solution, as the drug product does not contain anti-microbial preservatives or bacteriostatic agents. A sufficient excess of drug product is included in each vial to account for withdrawal losses.

The infusion of the reconstituted and diluted solution of elotuzumab for injection prepared for dosing must be completed within 24 hours of reconstitution. If not used immediately, the infusion solution may be stored under refrigeration conditions, 2°C to 8°C (36°F to 46°F), and protected from light for up to 24 hours (a maximum of 8 hours of the total 24 hours can be at room temperature, 20°C to 25°C (68°F to 77°F), and room light). The drug solution should be equilibrated to room temperature and the container must be gently inverted to mix well before administration.

9.1.7. Administration

Elotuzumab will be given cycle 1 & 2 at 10 mg/kg IV once a week (days, 1, 8, 15, and 22) in 28-day cycles.

From cycle 3 and beyond, elotuzumab will be given at 10mg/kg IV every two weeks (days 1 and 15) in 28-day cycles.

Elotuzumab should be initiated at an infusion rate of 0.5 mL per minute. If well tolerated, the infusion rate may be increased in a stepwise fashion as described in Table 5. The maximum infusion rate should not exceed 5 mL per minute. Please refer to section 6.3.1 for full infusion rate details for elotuzumab.

9.1.8. Ordering

The investigator or designee will order drug from Bristol-Myers Squibb, according to the ordering instructions provided by company.

9.1.9. Accountability

The investigator, or designee, is responsible for taking an inventory of each shipment of elotuzumab received, and comparing it with the accompanying accountability form. The Investigator, or designee, will verify the accuracy of the information on the form, sign and date it, retain a copy in the study fill. Accurate records will be kept in the source documentation of all drug administration (including dispensing and dosing).

9.1.10. Destruction and Return

IMP (those supplied by the sponsor or sourced by the site/investigator) are ideally to be destroyed on site. It is the Investigator's responsibility to ensure that arrangements have been made for the destruction, procedures for proper destruction have been established according to applicable regulations, guidelines and institutional procedures, and appropriate records of the destruction have been documented. The unused IMPs can only be destroyed after being inspected and reconciled by the responsible site monitor.

Ideally used IMP should not be returned to the Sponsor but destroyed on site. All unused and/or partially used IMP may be destroyed on site providing the site has an appropriate standard operating procedure on file.

If required by local country/hospital regulations IMP can be returned to a BMS off-site IMP destruction vendor, but this should only be arranged by your site monitor. All IMP destruction must be documented. If on-site destruction occurs, then a Confirmation of Destruction must be available at the site, in accordance with the local laws, regulations and institutional requirements. If IMP is returned for destruction off site, the Investigational Product Return Form acts as the destruction certificate. All related documentation must be filed.

9.2. Carfilzomib

9.2.1. Description

Carfilzomib is a synthetic small molecule peptide bearing the chemical name (2S)-N-((S)-1-((S)-4-methyl-1-((R)-2-methyloxiran-2-yl)-1-oxopentan-2-ylcarbamoyl)-2-phenylethyl)-2-((S)-2-(2-morpholinoacetamido)-4-phenylbutanamido)-4-methylpentanamide. The molecular formula is $C_{40}H_{57}N_5O_7$ and the molecular weight is 719.91. It specifically functions as an inhibitor of the chymotrypsin-like activity of the 20S proteasome, which leads to the accumulation of protein substrates within the cell and induction of apoptosis.

9.2.2. Formulation

Carfilzomib for Injection will be provided as a lyophilized powder which, when reconstituted, contains 2 mg/mL isotonic solution of carfilzomib Free Base in 10 mM sodium citrate buffer (pH 3.5) containing 10% (w/v) sulfobutylether--cyclodextrin (SBE--CD, Captisol®).

9.2.3.Storage

Lyophilized Carfilzomib for Injection must be stored at 2–8°C under the conditions outlined in the separate Pharmacy Manual, in a securely locked area to which access is limited to appropriate study personnel.

9.2.4. Accountability

Amgen, Inc. and the Site Investigator will maintain records of each shipment of investigational product. The records will document shipment dates, method of shipment, batch numbers, and quantity of vials contained in the shipment. Upon receipt of the investigational product, the designated recipient at the study site will inspect the shipment, verify the number and condition of the vials, and prepare an inventory or drug accountability record.

Drug accountability records must be readily available for inspection.

Empty and partially used vials should be accounted for and destroyed at the study site in accordance with the internal standard operating procedures. Drug destruction records must be readily available for inspection.

Only sites that cannot destroy unused drug on-site will be required to return their unused supply of investigational product.

